9.4.2 Secondary Endpoints

Secondary efficacy endpoints assess the effect of IV Ampion compared to SOC on the clinical outcomes for participants with COVID-19 on supplemental oxygen. The secondary endpoints will be tested in a hierarchical manner in the order presented, and thus no adjustment to the alpha level is necessary:

Objective	Endpoint
Secondary Endpoints	
Assess the effect of Ampion compared to placebo on safety	
Incidence of adverse events (AEs) and serious adverse events (SAEs) from baseline to Day 60.
Assess the effect of Ampion compared to placebo on clinical improvement	
Change in ordinal scale from baseline through Day 7.Change in ordinal scale from baseline to hospital discharge or day 14 (whichever occurs first).Change in ordinal scale from baseline to hospital discharge or day 28 (whichever occurs first).Change in NEWS2 score from baseline through Day 5.Change in NEWS2 score from baseline to hospital discharge.Modulation of cytokine levels from baseline to Day 5.
Assess the effect of Ampion compared to placebo on duration of respiratory failure to ventilator-free days.	
Percentage of participants who progress to respiratory failure (i.e., need for mechanical ventilation, ECMO, non-invasive ventilation) by Day 28.

Objective	Endpoint
Assess the effect of Ampion compared to placebo on intensive care	
Percentage of participants who require Intensive Care Unit (ICU) admission by Day 28.ICU-free days through Day 28.ICU LOS from ICU admission to discharge.
Assess the effect of Ampion compared to placebo on hospital stay	
Hospital length of stay (LOS) from admission to discharge.Hospital-free days through Day 28.
Assess the effect of Ampion compared to placebo on oxygen use	
Duration of oxygen use, blood oxygen saturation, and oxygen flow rate from baseline through Day 5.

The efficacy endpoints will be evaluated to estimate the treatment effect and use descriptive statistics including mean, standard deviation, percentages, minimum/maximum, and 95% confidence intervals. All endpoints will be tabulated and presented by treatment arm, cohort (severe and critical), and timepoint. Where appropriate, data will be tabulated and presented cumulatively across cohorts and/or timepoints.

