3.2 Secondary Endpoints

3.2.1 Change in ordinal scale from baseline through Day 7, Day 14 and Day 28.

The hypotheses to be tested are:

$$H_0: \mu_A = \mu_S \text{ versus } H_A: \mu_A \neq \mu_S$$

Where μ_A and μ_S represent the ordinal scale shift through day 7, 14, and 28 for Ampion and Placebo after randomization. The difference between Ampion and Placebo with respect to the change from baseline at day 7, 14, and 28 will be tested utilizing a Wilcoxon rank-sum test via PROC NPAR1WAY. To assess any potential time trends, an exploratory repeated measures analysis of variance will be performed with terms for treatment, time and the interaction between the two. This will be done utilizing PROC GLM with the REPEATED option.

3.2.2 Change in NEWS2 score from baseline through Day 7, or discharge if earlier.

The hypotheses to be tested are:

$$H_0: \mu_A = \mu_S \text{ versus } H_A: \mu_A \neq \mu_S$$

Where μ_A and μ_S represent the mean change from baseline in the NEWS2 score assessment through day 7 for Ampion and Placebo after randomization. The difference between Ampion and Placebo with respect to the change from baseline at day 7, or discharge if earlier, will be tested utilizing a Wilcoxon rank-sum test via PROC NPAR1WAY. To assess any potential time trends an exploratory repeated measures analysis of variance will be performed with terms for treatment, time and the interaction between the two. This will be done utilizing PROC GLM with the REPEATED option.

3.2.3 Percentage of participants who progress to respiratory failure by Day 28.

The hypotheses to be tested are:

$$H_0: \pi_A = \pi_S \text{ versus } H_A: \pi_A \neq \pi_S$$

Statistical Analysis Plan (SAP) for Clinical Study AP-017

Let π_A and π_S represent the percentage of patients who have respiratory failure for Ampion and control during the first 28 days after randomization.

This difference will be tested utilizing the appropriate chi-square test or Fisher's exact test utilizing PROC FREQ with the EXACT option, if needed.

Also, the median time to respiratory failure will be tested for difference between the two groups via the log-rank test. The log-rank test will be performed using PROC LIFETEST; and the estimation of the time-to-event distributions will be performed using the method of Kaplan and Meier.

3.2.4 Percentage of participants who require Intensive Care Unit (ICU) admission by Day 28; ICU-free days through Day 28; ICU length of stay (LOS) from ICU admission to discharge.

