There are two endpoints in this set. Hypotheses about both will be tested independently. The first hypothesis about the percentage of patients who are admitted to the ICU involves all patients. The second hypothesis involves only patients who are admitted to the ICU. Since it is not known how many many patients will be admitted to the ICU, the testing of the second hypothesis will be considered exploratory and not part of the hierachial testing scheme.

The first hypotheses to be tested is:

$$H_0: \pi_A = \pi_S \text{ versus } H_A: \pi_A \neq \pi_S$$

Where π_A and π_S represent the percentage of patients who are admitted to the ICU for Ampion and Placebo during the first 28 days after randomization. The difference between Ampion and Placebo will be tested via an appropriate chi-square test or Fisher's exact test utilizing PROC FREQ with the EXACT option, if needed.

The second hypothesis to be tested is:

$$H_0: \text{Median}_A = \text{Median}_S \text{ versus } H_A: \text{Median}_A \neq \text{Median}_S$$

Where Median_A and Median_S are the median ICU length of stay for the Ampion and placebo groups. Assuming there is no censoring, this will be tested using the Wilcoxon rank sum test via PROC NPAR1WAY. If censoring occurs, e.g., death, then the log rank test will be used based on PROC LIFETEST.

3.2.5 Modulation of cytokine levels from baseline to Day 5.

The hypotheses to be tested are:

$$H_0: \mu_A = \mu_S \text{ versus } H_A: \mu_A \neq \mu_S$$

Where μ_A and μ_S represent the mean percent change from baseline in the cytokine levels at day 5 for Ampion and Placebo after randomization. The difference between Ampion and Placebo with respect to the percent change from baseline at day 5 will be tested utilizing a two sample t-test via PROC TTEST. To assess any potential time trends an exploratory repeated measures analysis of variance will be performed with terms for treatment, time and the interaction of the two. This will be done utilizing PROC GLM with the REPEATED option.

Statistical Analysis Plan (SAP) for Clinical Study AP-017

3.2.6 Hospital length of stay.

The hypotheses to be tested are:

$$H_0: \text{Median}_A = \text{Median}_S \text{ versus } H_A: \text{Median}_A \neq \text{Median}_S$$

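### ICU-free days through Day 28 is a named secondary endpoint with no definition, test or table; the only ICU duration analysis is an exploratory length-of-stay test in admitted patients, which is not a randomised comparison.

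*SAP*

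**What the plan says.** The heading of SAP 3.2.4 names the percentage of participants needing ICU admission by Day 28 and then "ICU-free days through Day 28; ICU length of stay (LOS) from ICU admission to discharge". That makes three endpoints. The text below it opens: "There are two endpoints in this set. Hypotheses about both will be tested independently".

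The two it goes on to specify are:

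- **ICU admission.** "The first hypothesis about the percentage of patients who are admitted to the ICU involves all patients". The test is chi-square or Fisher's exact.
- **ICU LOS.** "The second hypothesis involves only patients who are admitted to the ICU". The test is Wilcoxon rank-sum, or log-rank if there is censoring, with death given as the example of censoring. Because the number of admissions is unknown, "the testing of the second hypothesis will be considered exploratory and not part of the hierachial testing scheme".

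ICU-free days does not appear again. It has no hypothesis or test in SAP 3.2, and no table, listing or figure of its own in SAP 10.

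Protocol 9.4.2 lists "ICU-free days through Day 28" and ICU LOS among the secondary endpoints tested hierarchically in the order shown. SAP 9, on changes from the protocol, says the secondary endpoints were put in hierarchical order. It does not mention dropping the ICU-free-days test or making ICU LOS exploratory.

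**The concern.** There are two linked problems.

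First, an endpoint that the protocol places in the hierarchy cannot be analysed as written. Neither document defines ICU-free days. The method rules in Protocol 9.4.2 cover binary, length-of-stay and change-from-baseline variables, and none clearly fits. Someone would have to choose the definition, the death rule and the test later, possibly after seeing data. Its place in the sequence is also unclear: SAP 8.6 tests in the order of Section 3.2, and cytokines (3.2.5) and hospital LOS (3.2.6) come after a heading that still names it.

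Second, the remaining duration test conditions on ICU admission, which the SAP itself tests as a treatment outcome. If Ampion changes which patients are admitted, the admitted patients in the two arms are no longer comparable. If it mainly prevents short stays, the patients left in its arm are the long-stay ones and LOS rises although nobody is worse off. Treating death as censoring adds a separate problem, because a patient who died is handled as though discharge from ICU were still to come. The subset also sits awkwardly with SAP 5.1.2, which puts all efficacy analyses in the ITT population.

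**Working it through.** **Figures in the plan.** The documents state no rate, stay or power for any ICU endpoint. The only power figure, 81.3% for the primary endpoint (8% against 22%, 100 per arm), reproduces at 81.28% by binomial enumeration with unpooled variances. It does not bear on this point. Everything below except the sample size of 100 per arm (SAP 2.4) is an assumption.

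**Hand example of the mechanism.** Placebo: 30 of 100 patients enter ICU, 15 for 4 days and 15 for 12 days. Ampion prevents the 15 short stays and cuts each long stay to 11 days.

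- LOS among admitted, placebo: (15 × 4 + 15 × 12) / 30 = 240 / 30 = 8.0 days.
- LOS among admitted, Ampion: (15 × 11) / 15 = 11 days, which looks worse.
- ICU days per randomised patient: 240 / 100 = 2.40 on placebo and 165 / 100 = 1.65 on Ampion.
- ICU-free days out of 28: 25.60 on placebo and 26.35 on Ampion, which is better.

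**Simulation.** 2,000 trials per scenario, 100 per arm, 35% ICU admission on placebo, stays gamma (shape 1.5, scale 8) capped at 28 days, no deaths. Wilcoxon on LOS among the admitted is compared with Wilcoxon on ICU-free days in all 200.

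| What Ampion prevents | Median LOS among admitted, Ampion minus placebo | LOS significantly longer on Ampion | ICU-free days significantly worse on Ampion |
|---|---|---|---|
| 60% of stays of 7 days or less | about +2.7 days | about 23% | under 1% |
| 25% of admissions, whatever the stay | about +0.1 days | about 2% (nominal) | under 1% |
| 40% of stays over 7 days | about −2.1 days | about 0.2% | under 1% |

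In the first row the expected gain in ICU-free days is 0.35 × 0.6 × E[stay; stay ≤ 7] = 0.35 × 0.6 × 1.41 ≈ 0.30 days per randomised patient (0.27 to 0.30 with simulation). ICU-free days is significantly better in only about 15% of those trials.

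**Sensitivity within the first scenario.** Placebo admission of 25% to 50% gives wrong-direction significance in 17% to 33% of trials. Preventing 30% to 80% of the short stays gives 8% to 41%.

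**A second model** (1,500 trials per scenario) lets stay rise with underlying severity and has the drug prevent the mildest admissions. With 30% admission on placebo, halved by the drug, and individual stays unchanged:

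- The LOS test has about 15 against 30 patients. Mean trial medians are 8.0 (Ampion) and 6.0 days, and LOS is significantly longer on Ampion in 32% of trials.
- ICU-free days averages 26.7 against 25.9. It is significantly better in 62% and significantly worse in 0.0%.
- If the halving is unrelated to severity, mean stays are 7.1 and 7.0 days, and wrong-direction significance falls to 2.7%.

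Over 20% to 40% placebo admission, risk ratios of 0.36 to 0.70 and stays shortened by 0 to 10%, the LOS test is significant in the wrong direction in 11% to 54% of trials. ICU-free days is significantly better in 17% to 96% and worse in at most 0.1%.

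Neither model includes death, so the bias from censoring deaths in the log-rank test is not quantified.

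**The case against.** The SAP already contains much of the damage. ICU LOS is exploratory and outside the hierarchy, so a misleading p-value cannot block or support another claim. The ICU test that stays in the hierarchy, admission by Day 28, uses all patients and would register prevented admissions, which is the mechanism at issue. A reader would see LOS beside that rate. All of this stands.

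Three stronger readings are tempting but not supported:

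- *The plan tests only the misleading ICU measure and omits the all-patient one.* It does test ICU admission in all patients. What is missing is an all-patient measure of duration.
- *Ampion would be made to look harmful.* That requires it to prevent mainly shorter stays. Nothing in the documents says so, and under the other two patterns the effect vanishes or reverses.
- *The ICU subset is formed entirely after randomisation.* Protocol 4.4 admits critical patients, including ventilated ones, so some may be in ICU at baseline. Neither document says how they count. Admission of the others is still open to treatment.

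Two cautions about the remedy are also fair. Scoring death as 0 days makes ICU-free days partly a mortality composite that overlaps the primary endpoint. It may also have little power. The case for it is that it compares the groups as randomised, not that it is more sensitive.

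What survives is the omission. The SAP's reason for the exploratory label is unknown numbers, not selection, and it still plans a p-value.

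**Conclusion.** The point holds as an unspecified endpoint together with a conditional caution. It is plain from the text that ICU-free days is named without a definition, test or table, that the protocol has it in the hierarchy, and that SAP 9 does not record the difference. It is equally plain that the only ICU duration test is confined to admitted patients and so is not a randomised comparison.

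The risk of a wrong-direction LOS result is illustrative. At 35% admission it ranges from about 0.2% to about 23% of trials across the three prevention patterns, and it reached 54% in the least favourable setting of the second model. It rests on assumed admission rates and stay distributions, on no deaths, and above all on whether prevented stays are the short ones. The consequence is limited to lower-order secondary endpoints and does not touch the primary analysis.

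**What to change.** In SAP 3.2.4, make the duration hypothesis ICU-free days through Day 28 in all randomised patients, and:

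- define it, with a stated rule for death by Day 28 (for example 0 days) and for patients already in ICU at baseline;
- test it by Wilcoxon rank-sum, preferably stratified by the randomised severity factor, and add a table to SAP 10;
- state its place in the hierarchy, reconcile Protocol 9.4.2 with SAP 3.2.4 on both ICU-free days and ICU LOS (including the LOS test, a t-test in one and Wilcoxon or log-rank in the other), and record the change in SAP 9;
- report ICU LOS among admitted patients descriptively, next to the number admitted and the deaths in each arm.

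The cost is SAP wording, plus whatever protocol wording the reconciliation needs. ICU admission and discharge dates and mortality are already collected under Protocol 5.2. The downside is that ICU LOS loses its own exploratory p-value.

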4. DEFINITIONS

4.1 Adverse Event:

An adverse event (AE) is defined as any undesired medical occurrence in a patient or clinical investigation patient receiving a pharmaceutical product and which does not necessarily have a causal relationship with this treatment. An AE can therefore be any unfavorable sign and unintended sign (including an abnormal laboratory finding), symptom, or disease temporarily associated with the use of a study drug, whether or not related to the study drug.

AEs will be graded for severity using the following categories. Missing grade will be assigned a grade of 3 (severe) in tabulations.

- **Grade 1 (MILD):** The symptom is barely noticeable to the study patient and does not influence performance or functioning. Concomitant medication is not ordinarily indicated for relief of mild AEs.
- **Grade 2 (MODERATE):** The symptom is of sufficient severity to make the study patient uncomfortable and to influence performance of daily activities. Concomitant medication may be indicated for relief of moderate AEs.
- **Grade 3 (SEVERE):** The symptom causes severe discomfort, sometimes of such severity that the study patient cannot continue in the study. Daily activities are significantly impaired or prevented by the symptom. Concomitant medication may be indicated for relief of severe AEs.

Relationship to study drug will be coded using the following categories. Missing relatedness will be assigned to related in tabulations.

- **Unrelated:** The adverse event is unlikely to have been caused by study drug.
- **Possibly related:** It is unclear whether the adverse event may have been caused by study drug.
- **Related:** The adverse event is likely to have been caused by study drug.

4.2 Serious Adverse Event:

A serious adverse event (SAE) is defined as an adverse event that

- Results in death
- Is life-threatening (patient is at immediate risk of death from the event as it occurred)

Statistical Analysis Plan (SAP) for Clinical Study AP-017

- Requires prolongation of existing hospitalization
- Results in persistent or significant disability/incapacity
- Results in a congenital anomaly/birth defect

4.3 Treatment-Emergent AE:

A treatment-emergent AE (TEAE) is any AE that begins or increases in severity after the initial dose of study drug.

4.4 Age:

Subject's age is defined as its integer value in years at enrollment.

4.5 Baseline:

For any variable, unless otherwise defined, baseline is the last assessment taken prior to the first study drug administration.

4.6 Change from Baseline:

The arithmetic difference between a post-baseline value and the baseline value:

Change from Baseline = (Post-baseline Value – Baseline Value)

Percentage Change from Baseline = [(Post-baseline Value – Baseline Value) / Baseline Value] x 100

4.7 End of Study:

End of study is at Day 60 unless terminated early.

4.8 Enrollment Date:

Enrollment date is the same as the randomization date and is designated Day 0.

4.9 Study Drug:

Study drug in this study is Ampion plus SOC or Placebo plus SOC.

4.10 Randomization Date:

Randomization date is the day the subject is assigned a randomization number on study Day 0.

4.11 Study Day 1:

Day 1 is defined as the first day that study drug is administered to the subject.

4.12 Study Day:

Day of treatment: study day = (visit date - date of Study Day 1 + 1)

5. ANALYSIS SUBSETS

5.1 Data Subsets

Statistical Analysis Plan (SAP) for Clinical Study AP-017

5.1.1 Safety Analysis Set

The safety analysis population is defined as all patients who are randomized and receive study treatment (Ampion or Placebo). Patients will be analyzed as treated. Summaries of data will include all data assigned to a nominal visit whether within the visit window.

5.1.2 Intent to Treat (ITT) Analysis Set

The intent-to-treat (ITT) analysis population is defined as all randomized patients. All efficacy analyses will be performed in the ITT population. Patients will be analyzed as randomized.

6. INTERIM ANALYSIS AND EARLY STOPPING GUIDELINES

6.1 Interim Analysis

This trial is designed to enroll up to approximately 200 subjects, randomized to active or control, following an equal allocation to treatment arms. An interim analysis of the data is planned after 30 subjects (approximately n=15 subjects per arm) to evaluate the relative treatment effect.

The interim analysis will be conducted on the primary and secondary endpoint data at an alpha level of 0.001 and thus the overall alpha level for the final test will be performed at approximately $\alpha=0.049$ instead of $\alpha=0.05$.

At the interim analysis, the sample size may be re-estimated to include additional subjects up to a total of 300 subjects to attain adequate power beyond the sample size of 200 originally calculated. This evaluation will be based on the methodology suggested by Gould et al. (Gould AL. Interim analyses for monitoring clinical trials that do not materially affect the type I error rate. Stat Med 1992; 11(1): 55-66) Let σ be the pooled rate of this study endpoint in the two arms, i.e. $\sigma=(p_{placebo}+p_{Ampion})/2$, where p is the incidence of the primary study endpoint in the respective groups. Let σ^* be the same value, but based on some assumed rates for these values from the beginning of the trial. Then the following sample size multiplier is determined:

$$f = [\sigma(1-\sigma)]/\sigma^*(1-\sigma^*)$$

If f is greater than 1, then the new sample size, n_1 , is determined as $f \times n$, where n is the original sample size (per group) of 100. If f is less than one, then the study will continue as originally envisioned.

The sponsor reserves the right to alter the final sample size if the assumptions of the rates of the primary endpoint are not satisfied at this interim analysis.

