9.2.3 Interim Analysis

This trial is designed to enroll up to approximately 200 subjects, randomized to active or control, following an equal allocation to treatment arms. An interim analysis of the data is planned after 30 subjects (n=15 subjects per arm) to evaluate the relative effect. At the interim analysis, the sample size may be re-estimated to include additional subjects to attain adequate power up to a 200 total subjects. This will be conducted at an alpha level of 0.001 and thus the overall alpha level for the final test will be performed at $\alpha=0.047$ instead of $\alpha=0.05$. The sponsor also reserves the right to alter the final sample size if the assumptions of the death rates are not satisfied at this interim analysis.

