2.4 Sample Size

The trial is designed to enroll up to approximately 200 patients across two treatment arms (active or control), with 100 subjects per arm, randomized 1:1 using a random allocation sequence stratified by COVID-19 disease severity (severe or critical). An interim analysis of the data is planned after 30 subjects (approximately n=15 subjects per arm) to evaluate the relative effect. At the interim analysis, the sample size may be re-estimated to determine the additional number of patients required for adequate power to meet the chosen effect size for the primary endpoint.

The number of participants is selected based on the effects observed for the primary endpoint, prevention of need for mechanical ventilation or death prior to day 28. A study recently reported in Lancet Respiratory Medicine with 243 hospitalized patients receiving the placebo for COVID-19 found 22% did not achieve day 28 ventilation-free survival (Lancet Respir Med 2021; [https://doi.org/10.1016/S2213-2600\(21\)00494-X](https://doi.org/10.1016/S2213-2600(21)00494-X)). In the AP-014 study, a lower rate (8%) was observed for subjects receiving inhaled Ampion. Assuming the same proportions (8% for Ampion and 22% for control) by Day 28, with 100 subjects per group, a two-sided 5% significance level, and using a z-test with unpooled variances, then under binomial enumeration the power to detect this difference is about 81.3%.

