6.2 Blinding Controls at Interim Analysis

The interim analysis will involve unblinded data. Only a small sequestered team will have access to the unblinded data and results. The data will not be transferred, or results viewed by any person involved in the day-to-day conduct of the clinical trial, including, but not limited to the blinded sponsor staff, Medical Monitor, and/or blinded CRO staff. These individuals will remain blinded to the results.

The unblinded team will be responsible for obtaining the required material for the analysis from the study's unblinded data manager (DM) for the clinical trial. The unblinded team will present

Statistical Analysis Plan (SAP) for Clinical Study AP-017

the results of the interim analysis to the sponsor in a blinded fashion (e.g., a simple recommendation to increase sample size or keep sample size as defined in the SAP without presenting the details surrounding the raw data, results, or efficacy conclusions).

All individuals on the sequestered team who are unblinded will be documented and archived by the sponsor.

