6.3 Stopping Rules

The study may be stopped upon recommendation by the safety monitoring committee.

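### The 0.001 efficacy test at the 30-patient interim has no stated consequence, is very unlikely to be met at the planned rates, and is not needed for the sample-size re-estimation

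*SAP*

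**What the plan says.** **The look.** SAP 6.1: "An interim analysis of the data is planned after 30 subjects (approximately n=15 subjects per arm) to evaluate the relative treatment effect". The same section adds: "The interim analysis will be conducted on the primary and secondary endpoint data at an alpha level of 0.001". Protocol 9.2.3 plans the look at the same point and says "This will be conducted at an alpha level of 0.001", without naming endpoints. The final alpha becomes about 0.049 in the SAP and 0.047 in the Protocol.

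**The re-estimation.** SAP 6.1 defines σ as the average of the two arms' primary event rates. It sets f = σ(1−σ) / [σ*(1−σ*)], with σ* taken from rates assumed at the start, and multiplies the 100 per arm by f when f exceeds 1.

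**Blinding.** SAP 6.2: "The interim analysis will involve unblinded data". Access is confined to a small sequestered team, whose membership is documented. The sponsor's blinded staff, the medical monitor and blinded CRO staff stay blinded. The message to the sponsor is described, by way of example, as "a simple recommendation to increase sample size or keep sample size as defined in the SAP", without efficacy conclusions.

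**Stopping.** SAP 6.3 has one rule: "The study may be stopped upon recommendation by the safety monitoring committee". Protocol 6.1 and 10.9 add safety grounds and sponsor discretion. None of these refers to the 0.001 threshold.

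**The concern.** An interim efficacy test is normally paid for in alpha because something is done when it is met. Here alpha is charged but no action is written down. With so few patients, the threshold also looks almost out of reach on the primary endpoint.

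The test has two effects. It lowers the final significance level, and it means that arm-level primary and secondary results exist after 30 of about 200 patients with no stated decision that uses them. If the threshold were met, the sequestered team would hold a result with no instruction on what to do with it.

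**Working it through.** **Inputs.** From SAP 2.4: "Assuming the same proportions (8% for Ampion and 22% for control) by Day 28, with 100 subjects per group, a two-sided 5% significance level", "using a z-test with unpooled variances", by binomial enumeration, stated power 81.3%. From SAP 3.1: a two-sided hypothesis, tested by chi-square or Fisher's exact test. From SAP 6.1: 15 per arm and alpha 0.001, taken here as two-sided.

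**1. The plan's own figure.** Power = Σ Bin(i; 100, 0.08) × Bin(j; 100, 0.22) over all (i, j) with p ≤ 0.05. With the unpooled z-test this gives 81.28%, which reproduces the stated 81.3%.

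**2. What crossing would take.** Expected events at the interim are 15 × 0.08 = 1.2 on Ampion and 15 × 0.22 = 3.3 on placebo. With no Ampion events:

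| Placebo events of 15 | Pearson p | Fisher p |
|---|---|---|
| 7 | 0.0025 | not needed |
| 8 | 0.00096 | 0.0022 |
| 9 | below 0.001 | 0.0007 |

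Pearson therefore needs at least 0 vs 8 and Fisher at least 0 vs 9.

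**3. Chance of crossing on the primary endpoint.** The same enumeration with 15 per arm and p ≤ 0.001:

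| True rates, Ampion vs placebo | Pearson | Fisher |
|---|---|---|
| 8% vs 22% (design) | 0.23% | 0.05% |
| 0% vs 22% (assumed) | 0.78% | 0.16% |
| 8% vs 30% (assumed) | 1.6% | 0.5% |
| 8% vs 40% (assumed) | 7.6% | 3.1% |

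At the design rates:
- A one-sided 0.001 would give 0.29% and 0.06%.
- Arms of 14 and 16, either way round, give 0.10% to 0.15%.
- 17 Ampion and 13 placebo gives at most 0.38%.
- The unpooled z-test, which the plan uses only for sizing, would give 0.92%.

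**4. Secondary endpoints.** The documents give no effect sizes or standard deviations, so no chance of crossing can be derived. As an illustration under assumed effects, a two-sample t-test (the method for cytokines in SAP 3.2.5) with 15 per arm at two-sided 0.001 has power of about 2%, 21% and 66% at standardized differences of 0.5, 1.0 and 1.5.

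**5. Whether the re-estimation needs treatment codes.** With 15 per arm, σ = (a/15 + b/15)/2 = (a + b)/30, which is the blinded total over 30. The SAP gives no number for σ*; the design rates imply (0.08 + 0.22)/2 = 0.15, so σ*(1−σ*) = 0.1275.
- 4 events: f = 0.1333 × 0.8667 / 0.1275 = 0.91, so keep the sample size.
- 5 events: f = 0.1667 × 0.8333 / 0.1275 = 1.09, so increase it. The chance of 5 or more events at the design rates is 48%.

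With arms of 14 and 16 the average of the arm rates is not exactly the total over 30, but the direction is the same. Four events give σ of at most (4/14)/2 = 0.143, and five give at least (5/16)/2 = 0.156, on either side of 0.15.

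**6. Cost in final power,** 100 per arm, 8% vs 22%:

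| Final alpha | Pearson | Fisher |
|---|---|---|
| 0.05 | 81.3% | 75.8% |
| 0.049 (SAP) | 81.2% | 74.9% |
| 0.047 (Protocol) | 80.2% | 74.2% |

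Under a bivariate normal approximation at information fraction 30/200, spending 0.001 at the interim leaves 0.0493 for the final test. The SAP's 0.049 is therefore adequate. The Protocol's 0.047 gives a total of about 0.048.

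**The case against.** The strongest reply is that this is an ordinary conservative safeguard: a tiny alpha for an unblinded look, a correctly reduced final level, and good controls on access. Much of that stands. The SAP's 0.049 is sound, its power cost with Pearson is 81.3 − 81.2 = 0.1 point, and the Fisher drop is partly a step caused by discreteness, since power is still 75.8% at 0.0495. The larger losses come from the Protocol's 0.047, which conflicts with the SAP and needs reconciling in its own right. SAP 6.2 does confine the unblinding.

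A reader might also infer three stronger things that the documents do not support.
- **That the test cannot succeed, or that 0.2% is a ceiling.** The figure belongs to one pair of rates. The 22% comes from a single external placebo group, and Protocol 4.4 admits critical patients, so a higher placebo rate is possible. Nothing can be computed for the secondary endpoints.
- **That a sample-size recommendation is the only message allowed out.** SAP 6.2 offers it as an example, SAP 6.3 does not limit the committee's grounds, and Protocol 10.9 lets the sponsor terminate for any reason. What can be said is that no action is specified on crossing.
- **That the whole interim serves no purpose.** The re-estimation is a real decision with about an even chance of changing the sample size at the design rates.

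The blinded total equals the SAP's σ exactly only with equal arms; the SAP says approximately 15 per arm. Section 5 of the working suggests that this matters little for a near-equal split.

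**Conclusion.** The concern holds in a limited form. The plan charges alpha for an interim efficacy test to which neither document attaches a consequence. On the primary endpoint at the planned rates, that test has a 0.23% (Pearson) or 0.05% (Fisher) chance of being met. The unblinding it requires is not needed for the only interim decision that is specified.

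The direct cost is modest: 0.1 point of power with Pearson and 0.9 with Fisher under the SAP's alpha, and 1.1 and 1.6 under the Protocol's. The better reason to act is that arm-level efficacy results would exist mid-trial without a rule for using them. The figures assume a two-sided 0.001, arms of 15, and 8% vs 22%. The argument about the missing action depends on none of these and covers the secondary endpoints too.

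**What to change.** In Protocol 9.2.3 and SAP 6.1 and 6.2:
- Delete the 0.001 test of primary and secondary endpoints.
- Base the re-estimation on the blinded pooled count, with σ defined as total primary events over total patients, and state the value of σ*.
- Set the final primary test at two-sided 0.05 in both documents. This also removes the conflict between 0.047 and 0.049.
- Leave unblinded safety review to the DSMB described in Protocol 3.5.

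The cost is a wording change. The sponsor gives up an early efficacy look that is very unlikely to be met on the primary endpoint at the planned rates and has no decision rule. If the sponsor wishes to keep the look, the gap can instead be closed by stating which endpoint is tested, what follows if the threshold is crossed and who decides, with one final alpha in both documents. That option keeps the mid-trial unblinding and the reduced final level.
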